3.3 Rationale of dose/regimen, route of administration and duration of treatment

Based on safety data from the PARADIGM-HF single-blind, sequential design run-in period, LCZ696 was well-tolerated, with over 90% of patients achieving the target dose.

A strong rationale exists for the target dose of LCZ696 in HF-rEF patients. A p.o. dose of LCZ696 200 mg bid delivers similar exposures of valsartan (assessed by AUC) as Diovan® 160 mg bid, the highest approved Diovan® dose for HF and the dose recommended in international guidelines for the treatment of HF. In addition, biomarker analysis (increase in ANP and cGMP) indicates that this dose delivers approximately 90% of its maximal NEP inhibition.

Most importantly, this study will target the oral dosing regimen for LCZ696 identical to that which showed a mortality and HF hospitalization benefit superior to that of enalapril in PARADIGM-HF.

[*] The study will continue in an individual country for a minimum of 12 months and until a marketing authorization has been received and the drug product becomes commercially available in that country (which is expected to be up to 30 months) from the date of the first eligible patient enrolled in that country, or until the study is terminated, whichever comes first. Within the study period, the duration of treatment for an individual patient will be at the discretion of the investigator.

[* For **Denmark only**, the above paragraph will read as follows:

From the date of the first eligible patient enrolled in Denmark, the study will have a duration of 12 months. The treatment duration may be re-evaluated and an amendment issued to adjust the treatment duration.]

[* For the **United Kingdom only** the above paragraph will read as follows:

From the date of the first eligible patient enrolled in the UK, the study has a minimum duration of 12 months and a maximum duration of 20 months. The treatment duration may be re-evaluated and an amendment issued to adjust the treatment duration].

[* For **Germany only**, the above paragraph will read as follows:

From the date of the first eligible patient enrolled in Germany, the study will have a maximum duration of 24 months. The treatment duration may be re-evaluated and an amendment issued to adjust the treatment duration.]

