5.5.9 Discontinuation of study treatment

Permanent discontinuation of LCZ696 constitutes withdrawal from the study. Under these circumstances, the patient should be evaluated at a final study visit but will not undergo assessments thereafter unless additional follow-up is required due to prior occurrence of an adverse event.

The investigator must also notify the IRT of the patient's discontinuation of LCZ696 and record it on the Drug Administration Record of the eCRFs.

The emergence of the following circumstances will require study drug discontinuation:

- Withdrawal of informed consent
- Pregnancy ([Section 6.5.6](#) and [Section 7.6](#))
- Investigator thinks that continuation would be detrimental to the patient's well-being

Study medication may be discontinued at the investigator's discretion if any of the following occurs:

- Any severe suspected drug-related AE
- Suspected occurrence of angioedema. A patient with any signs or symptoms of clinically significant angioedema should be thoroughly evaluated by the investigator and constitute a reason for discontinuation of study medication.

Depending on the serum potassium, blood pressure, or eGFR, patients may need to have their LCZ696 dose or the dose of another concomitant medication reduced or discontinued, or, if appropriate, have potentially contributing agents adjusted. Please refer to [Appendix 3](#), [Appendix 4](#) and [Appendix 5](#) for treatment guidelines for hyperkalemia, hypotension, or renal dysfunction, respectively.

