5.5.14 Early study termination

The study can be terminated at any time for any reason by Novartis. Should this be necessary, the patient should be seen as soon as possible and treated for a prematurely withdrawn patient. The investigator may be informed of additional procedures to be followed in order to ensure that adequate consideration is given to the protection of the patient's interests. The investigator will be responsible for informing the Institutional Review Board/Independent Ethics Committee (IRBs/IECs) of the early termination of the trial.

6 Visit schedule and assessments

Following start of LCZ696 treatment (at Visit 1, or at the time of successfully complete the rescreening visits), initial visits up to the visit at 3 months (Visit 4) are set a relatively short interval. The subsequent visits will occur at intervals of 6 months beginning at Visit 6.

Visits 2 should be conducted between 1-to-2 weeks after starting treatment with LCZ696. Visit 3 should be conducted between 2-to-4 weeks and at least 1 week after Visit 2.

Visits 4 through 9 within +/- 7 days of the designated calendar day according to Table 6-1 or as close to it as possible. Specific circumstances surrounding missed or rescheduled visits

must be discussed with the study monitor. Missed or rescheduled visits SHOULD NOT LEAD automatically to patient discontinuation.

Patients should take their scheduled dose of LCZ696 in the morning of their study visits. Patients are not required to fast overnight on the day prior to or the day of the study visit.

The Assessment Schedule ([Table 6-1](#)) lists the assessments to be conducted at each of the study visits (indicated with an “x”).

For patients, who discontinue LCZ696, the discontinuation visit will be Visit 9 (EOS). Enrolled patients who withdraw from the study for any reason, should be scheduled for a visit as soon as possible, at which time all of the assessments listed for Visit 9 (EOS) will be performed. At this final visit all dispensed medication supplies should be reconciled and the Adverse Events and Heart Failure Medications updated on their respective CRFs.

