All data obtained from the assessments listed in [Table 6-1](#) must be supported in the patient’s source documentation. The table indicates which data are entered into the CRF from the source data (D), remain in the source documents only (S) or are loaded into the database from separate source documents, i.e. outside vendors (DS). Assessments that generate data for database entry and which are recorded on CRFs are listed using the CRF name.

Table 6-1 Assessment schedule

Epoch		Epoch I Screening	Epoch II Open-label Treatment							
			101	102	103	104	105	106	107	199
Database visit numbering		1	2	3	4	5	6	7	8	9 ² EOS and ITD
Visit ¹		1 *	2	3	4	5	6	7	8	9 ² EOS and ITD
Time	Category	0	1-2 w after start dose	2-4 w	3 m §	6 m §	12 m §	18 m §	24 m	30 m §
Pregnancy test (urine dipstick) ⁶	S	X				X	X	X	X	
Pregnancy test (serum) ⁶	S	X								X
Prior/Concomitant heart failure medications	D/S	X	X	X	X	X	X	X	X	
Adverse events	D/S		X	X	X	X	X	X	X	
Dispense study medications	D/S	X	X	X	X	X	X	X	X	
Drug accountability	S		X	X	X	X	X	X	X	

EOS = end of study; ITD = investigational treatment discontinuation; D = assessment to be recorded on clinical data base; S = assessment to be recorded in source documentation; DS = data transferred from vendor

[§] Within +/- 7 days of the designated calendar day

¹ Unscheduled visits may occur if a safety issue develops

² if a patient fails screening to qualify for the study at Visit 1, s/he may repeat Visit 1 up to two times in order to participate in the study.

³ Visit 9 (End of Study visit) will be completed at approximately 30 months or if the patient permanently discontinues LCZ696 or withdraws early from the study between Visit 1 and Visit 8 or when marketing authorizations are obtained and the product becomes commercially available in the patient's country.

⁴ IRT will be used to enroll patients into the study, dispense open-label medication, track visit dates and record completion or early withdrawal from the trial.

⁵ Height will be measured at Visit 1 only.

⁶ Abbreviated laboratory assessments (performed locally) include serum sodium, potassium and creatinine measured at Visits 2, 3, 4, 7 and 9. At Visits 5, 6 and 8 local labs will include serum sodium, potassium, creatinine, ALT, AST, alkaline phosphatase and total bilirubin.

⁷ Pregnancy testing performed in women of child-bearing potential only, see Section 6.5.6.

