6.5.4 Laboratory evaluations

Laboratory samples will be analyzed locally. Values outside the normal ranges and notable values should be flagged on the report. It is the responsibility of the investigator to review all laboratory results and make an assessment of whether an abnormal or notable value is clinically significant, whether additional evaluations should be performed as judged appropriate, and whether the patient may continue in the trial. Sample collection should be conducted according to the standards and requirements of the local laboratory.

- Laboratory values that exceed the boundaries of a notable laboratory abnormality (refer to [Appendix 1](#)) must be commented on by the investigator in the source documents and additional laboratory evaluations should be performed, as judged appropriate by the investigator.
- If the laboratory abnormality induces clinical signs or symptoms, or requires therapeutic intervention, and satisfies the criteria defined in [Section 7.1](#), then the diagnosis or medical condition must be entered on the AEs page of the patient's eCRF and any treatment necessary should be documented. If the laboratory abnormality is the primary reason for an unforeseen hospitalization or otherwise fulfills the seriousness category of an AE, then the procedure for rapid notification of SAEs must be followed.
- Likewise, if the laboratory abnormality leads to discontinuation of the study drug, the patient must be followed until the abnormality resolves or until it is judged to be permanent. This investigation may include continued monitoring by repeat laboratory

testing or by performing additional laboratory tests as deemed necessary by the investigator or the Sponsor's medical monitor.

Clinically notable laboratory findings are defined in [Appendix 1](#).

Full laboratory clinical chemistry ([Table 6-2](#)) will be performed locally at Visit 1 and abbreviated laboratory evaluations (sodium, potassium, creatinine) will be performed locally at Visits 2, 3, 4, 7 and 9. At Visits 5, 6 and 8 local labs will include sodium, potassium, creatinine, ALT, AST, alkaline phosphatase and total bilirubin.

Full laboratory tests will include the following:

Table 6-2 Full laboratory evaluations

Biochemistry
Sodium
Potassium
BUN
Creatinine
Total bilirubin
AST
ALT
γ GT
Alkaline phosphatase
Creatine phosphokinase (CPK)
Uric acid
Total protein
Albumin

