8.3 Database management and quality control

The Sponsor's staff review the data entered into the CRFs by investigational staff for completeness and accuracy and instruct the site personnel to make any required corrections or additions. Queries are sent to the investigational site using an electronic data query. Designated investigator site staff is required to respond to the query and confirm or correct the data. If the electronic query system is not used, a paper Data Query Form will be faxed to the site. Site personnel will complete and sign the faxed copy and fax it back to the Sponsor's staff that will make the correction to the database. The signed copy of the Data Query Form is kept at the investigator site.

Concomitant heart failure medications entered into the database will be coded using the WHO Drug Reference List, which employs the Anatomical Therapeutic Chemical classification system. Adverse events will be coded using the Medical dictionary for regulatory activities (MedDRA) terminology.

Laboratory samples will be analyzed locally. The data will be recorded in source documents but will not be entered into the clinical database.

Data about LCZ696 dispensed to the patient and all dosage changes will be tracked using an Interactive Response Technology (IRT). The system will be supplied by a vendor, who will also manage the database. The database will be sent electronically to Novartis (or a designated CRO).

The occurrence of relevant protocol deviations will be determined. After these actions have been completed and the database has been declared to be complete and accurate, it will be locked and made available for data analysis. Any changes to the database after that time can only be made after written agreement by the Sponsor's Development management.

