SOLVD Investigators (1992) Effect of enalapril on mortality and the development of heart failure in asymptomatic patients with reduced left ventricular ejection fractions. *N Engl J Med*; 327:685-691.

13 Appendix 1: Clinically notable laboratory values

Clinically notable laboratory abnormalities for selected tests based on a percent change from baseline:

Hematology

RBC count	>50% increase, >20% decrease
Hemoglobin	>50% increase, >20% decrease
Hematocrit	>50% increase, >20% decrease
WBC count	>50% increase, >50% decrease
Platelet count	>75% increase, >50% decrease

Blood Chemistry

ALT (SGPT)	>150% increase
AST (SGOT)	>150% increase
BUN	>50% increase
Creatinine	>50% increase
Total bilirubin	>100% increase
CPK	>300% increase
Alkaline phosphatase	>100% increase
Sodium	>5% decrease
Potassium	>20% increase, >20% decrease
Uric acid	>50% increase

14 Appendix 2: Liver event and laboratory trigger definitions and follow-up requirements

Table 14-1 Liver event definitions

Definition/ threshold	
AE of special interest	
Laboratory values	ALT or AST > 3 x ULN ALP > 2 x ULN TBL > 1.5 x ULN
Medically significant event (SAE)	
Laboratory values	ALT or AST > 5 x ULN (with or without TBL > 2 x ULN [mainly conjugated fraction]) ALP > 5 x ULN (with or without TBL > 2 x ULN [mainly conjugated fraction]) TBL > 3 x ULN Potential Hy's Law cases (defined as ALT/AST > 3 x ULN and TBL > 2 x ULN [mainly conjugated fraction] without notable increase in ALP to > 2 x ULN)
AEs	Any clinical event of jaundice (or equivalent term) ALT or AST > 3 x ULN accompanied by general malaise, fatigue, abdominal pain, nausea, or vomiting, or rash with eosinophilia Any event that links to a preferred term (PT) in the MedDRA dictionary falling under the SMQ sub-module "Drug-related hepatic disorders – severe events only"** or any "Hy's law case" PT

* These events cover the following: hepatic failure, fibrosis and cirrhosis, and other liver damage-related conditions; the non-infectious hepatitis; the benign, malignant and unspecified liver neoplasms

Table 14-2 Liver event follow up requirements

Criteria	Event type	Actions required	Follow-up monitoring

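### Liver tests are not scheduled at the exit visit (Visit 9), so patients who stop before month 6 leave with no scheduled post-baseline liver test

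*Protocol*

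**What the plan says.** Protocol 6.5.4 schedules full chemistry, with liver tests, at Visit 1. It then says that "abbreviated laboratory evaluations (sodium, potassium, creatinine) will be performed locally at Visits 2, 3, 4, 7 and 9". ALT, AST, alkaline phosphatase and total bilirubin are added only at Visits 5, 6 and 8. Protocol 6.5.4.2 and the laboratory footnote to Table 6-1 give the same lists.

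Visit 9 is more than the month-30 visit. A footnote to Table 6-1 says that "Visit 9 (End of Study visit) will be completed at approximately 30 months or if the patient permanently discontinues LCZ696"; it also covers early withdrawal and the point at which the product reaches the market in the patient's country. Protocol section 6 has all withdrawing patients complete the Visit 9 assessments. Under Protocol 5.5.9, permanent discontinuation counts as withdrawal, and "the patient should be evaluated at a final study visit but will not undergo assessments thereafter", apart from follow-up of an earlier adverse event.

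Protocol 3.3 sets country limits counted from the first patient enrolled in that country. For the UK, "the study has a minimum duration of 12 months and a maximum duration of 20 months"; for Germany, "the study will have a maximum duration of 24 months". Both may be changed by amendment.

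On the local laboratory results, Protocol 8.3 says: "The data will be recorded in source documents but will not be entered into the clinical database".

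**The concern.** Section 7.3 relies on Appendix 2 to identify liver events. In Table 14-1 every liver event of special interest is a laboratory threshold (ALT or AST above 3 x ULN, alkaline phosphatase above 2 x ULN, bilirubin above 1.5 x ULN). Several serious liver events are also defined by laboratory values alone, including potential Hy's Law cases. An asymptomatic patient who is not tested cannot meet any of these.

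Omitting liver tests at Visit 7 matters less, because a patient who continues is tested at Visit 8. A patient who leaves has no later visit, and the adverse-event exception in 5.5.9 cannot be triggered by an elevation that nobody measured. Such a patient would leave without the repeat tests, causality assessment and reporting that Table 14-2 sets out.

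Safety is the primary objective and there is no data monitoring committee (8.4). Anyone with one dose is in the Safety set (9.1), so untested early leavers count in the denominator for serious adverse events.

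This is a gap in the sampling schedule, not a contradiction: section 7.3 does not itself call for tests at exit.

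**Working it through.** The plan gives no figure to reproduce here; the check is on the visit schedule.

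**Inputs.** Scheduled liver tests at months 0 (Visit 1), 6 (Visit 5), 12 (Visit 6) and 24 (Visit 8), from Protocol 5.5.4 and 6.5.4. Exit is at Visit 9, without liver tests. Visits 4 to 9 have a window of 7 days either side, so month boundaries are approximate.

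**Formula.** Gap at exit = exit month − month of the last scheduled liver test.

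| Exit month | Scheduled post-baseline liver tests | Time since the last one |
|---|---|---|
| before 6 | 0 | none after baseline |
| 6 to 12 | 1 (Visit 5) | up to 6 months |
| 12 to 18 | 2 (Visits 5, 6) | up to 6 months |
| 18 to 24 | 2 (Visits 5, 6) | 6 to 12 months |
| 24 to 30 | 3 (Visits 5, 6, 8) | up to 6 months |

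A patient who completes the full course exits 30 − 24 = 6 months after the last liver test.

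**Country limits.** Let L be the months between the first patient's enrolment in a country and a given patient's enrolment. The documents do not give L, so the values below are assumptions.

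- UK, 20-month cap: exit at 20 − L, last test at month 12, gap 8 − L. This is 8 months for the first patient (L = 0) and 6 at L = 2. It is below 6 for later enrolment up to L = 8.
- Germany, 24-month cap, 0 < L ≤ 6: exit at 24 − L, before Visit 8 is due, gap (24 − L) − 12 = 12 − L. For L = 1, 3 and 6 the gap is 11, 9 and 6 months. For the first patient the cap coincides with Visit 8. The gap is up to 12 months only if Visit 9 replaces Visit 8, which the documents do not state.
- Denmark, 12-month duration: exit at 12 − L. For L > 6 this is before month 6, so there is no post-baseline liver test.

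**Patients affected before month 6.** The documents give no stopping rate. Assuming a share of the planned 5,000 stop before Visit 5 and attend Visit 9: 5,000 × 0.02 = 100; 5,000 × 0.05 = 250; 5,000 × 0.10 = 500.

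**With liver tests at Visit 9.** Every patient who attends has at least one scheduled post-baseline liver test. Those who stop before Visit 5 go from 0 to 1.

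**The case against.** The schedule is consistent in three places and looks deliberate. Protocol 6.5.7 says the safety measurements resemble those of PARADIGM-HF and suit the profile in the Investigator Brochure, which is not available here. The documents name no hepatic signal. The risks given as examples in 3.6, the focus of dose adjustment in 5.5.5 and the tabulated events of special interest in 9.4 and SAP 9.7.1.6.1 are all hypotension, hyperkalemia and renal dysfunction, which the exit panel and vital signs cover. Patients had to pass the PARADIGM-HF run-in and have ALT and AST no higher than 3 x ULN at Visit 1. Clinical liver events can still be found through questioning, examination at Visit 9, unscheduled tests and sponsor requests. A patient who has discontinued has already stopped the drug, which is the main action in Table 14-2. No exit gap exceeds the 12 months between Visits 6 and 8 that the protocol accepts on treatment.

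Much of this stands. It limits the gap to asymptomatic, laboratory-only elevations and keeps the point from being a major one. The absence of an elevation rate also means that the number of missed events cannot be estimated; the patient counts above are leavers, not missed cases.

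It does not close the gap. A patient on treatment who goes 12 months untested is then tested; a leaver is not. Table 14-2 asks for more than stopping the drug: repeat tests, causality work and, for the serious categories, reporting. Patients who exit at month 30 or at commercial availability have not stopped for tolerability. Section 6.5.7 gives no reason for leaving liver tests out at exit.

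**Conclusion.** The concern holds. A patient who leaves before Visit 5 has no scheduled post-baseline liver test. Later leavers have a gap of up to 6 months, or 6 to 12 months for exits in months 18 to 24. This follows directly from the schedule. The country-cap figures rest on assumed enrolment lags and on caps that may be amended, and the counts of 100 to 500 patients rest on assumed stopping rates.

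The consequence is for patient safety and for capture of laboratory-defined liver events. A serious one found at exit would be reportable, since the reporting period runs to 30 days after the last dose (7.2.2). The planned laboratory and special-interest tables are unaffected, because laboratory values stay in source documents and liver events are not among the tabulated special-interest categories. It is a worthwhile, inexpensive improvement that should be made, not a flaw that undermines the study.

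**What to change.** In Protocol 6.5.4, 6.5.4.2 and the laboratory footnote to Table 6-1, take Visit 9 out of the list of Visits 2, 3, 4, 7 and 9 and add it to the list of Visits 5, 6 and 8. Sodium, potassium and creatinine are kept, and ALT, AST, alkaline phosphatase and total bilirubin are run on the same sample. Appendix 2 needs no change.

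The cost is a wording change and four local analytes once per patient, at most 4 × 5,000 = 20,000 results, with no extra visit or blood draw. There will be some additional follow-up under Table 14-2. For patients who discontinue, the result may come shortly after the last dose rather than on treatment, so it is a slightly less direct reading of on-drug liver function.

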6.5.4.1 Hematology

Hematology will not be performed in this study unless requested by the investigator as part of the patient's Standard of Care (conducted locally).

6.5.4.2 Clinical chemistry

Sodium, potassium, BUN, creatinine, total bilirubin, AST, ALT, γGT, alkaline phosphatase, CPK, uric acid, total protein, and albumin and will be measured as full laboratory evaluations at Visit 1 ([Table 6-1](#)).

The eGFR to determine eligibility of the patient for screening into the trial will be calculated at Visit 1 from the serum creatinine concentration. Estimated GFR will only be calculated using the following formula:

Estimated GFR (mL/min/1.73 m²) = 175 × (standardized S_{Cr} in mg/dL)^{-1.154} × (age in years)^{-0.203} × (0.742 if female) × (1.212 if black), where S_{Cr} is the standardized serum creatinine value

Abbreviated laboratory evaluations (sodium, potassium and creatinine) will be performed at Visits 2, 3, 4, 7 and 9. At Visits 5, 6 and 8 the abbreviated laboratory evaluations will

include sodium, potassium, creatinine, ALT, AST, alkaline phosphatase and total bilirubin. Fasting is not required prior to the blood sampling for assessment of these laboratory parameters.

If a patient experiences liver function test (i.e. ALT, AST, ALP, TBL) values greater than three times the upper limit of normal during the study, additional information may be collected. See [Appendix 2](#) for the follow-up requirements.

